1. All study visits will be scheduled relative to the Baseline visit, with an allowable variance of ± 3 days for each visit (with the exception of the Screening and the Safety Follow-up Visits) to accommodate scheduling. All Screening/Baseline assessments and inclusion/exclusion criteria must be satisfied prior to randomization and dosing. The Screening Visit window may be up to 8 weeks for *PHEX* mutation analysis and washout of oral phosphate and active vitamin D therapy. KRN23 dosing should occur no sooner than 8 days since the last dose administered.
2. *PHEX* mutation analysis will be performed in all subjects. Potential subjects with prior confirmation of a *PHEX* mutation or variant of uncertain significance in either self or a family member with appropriate X-linked inheritance who meet other eligibility requirements may enroll before screening *PHEX* mutation results are returned.
3. Patients will be randomized 1:1 to either the KRN23 treatment arm or the active control arm (oral phosphate/active vitamin D therapy).
4. Active control will be administered at the discretion of the treating Investigator. Subjects randomized to the active control arm will visit the clinic at Weeks 1, 4, 8, 16, 24, 32, 40, 52, and 64. Active control will be discontinued after the Week 64 visit to allow washout of oral phosphate and active vitamin D treatments before the first dose of KRN23 at Week 66 for subjects originally randomized to active control.
5. In subjects < 2 years old, recumbent length will be measured instead of standing and sitting height. At each time point, height will be assessed 3 times and each assessment will be recorded onto the subject chart and eCRF. An average of the 3 measurements will be calculated. Pre-study recumbent length/standing height data will be collected as discussed in Section 7.5.1.
6. Screening results will be treated as Baseline data.
7. AP knee and PA hand/wrist x-rays will be acquired for all subjects and standing long leg x-rays will be acquired for all qualifying subjects. Pre-study radiographs will be collected as discussed in Section 7.5.1.
8. 6MWT will be conducted only for subjects ≥ 5 years of age at the Screening Visit. If a subject is < 5 years of age at the Screening Visit, the 6MWT will not be assessed when the subject is over 5 years of age during the post-baseline visits.

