14. Vital sign measurements consist of seated systolic/diastolic blood pressure (BP) measured in millimeters of mercury (mm Hg), heart rate (beats per minute), respiration rate (breaths per minute), and temperature in degrees Celsius (°C). Vital signs will be obtained at the beginning of each visit before any additional assessments are completed and after the subject has rested for 5 minutes. BP measurements will only be obtained at clinic visits and only for subjects ≥ 3 years of age. At the Screening Visit and at Baseline, 2 sets of 3 BP measurements will be obtained – the first set will be done at the beginning of the visit and the second set at end of the visit after all site procedures are completed. BP measurements should be obtained by auscultation (ie, manually and without using an automated device) after the subject has rested for 5 minutes and a second and third BP measurement should be obtained, each performed 30 seconds apart.
15. The subject's weight collected at in-clinic visits will be the basis of the KRN23 dose calculation until the next in-clinic weight collection.
16. Adverse events and concomitant medications information will be collected at HH visits for subjects in the KRN23 arm during the Treatment Period and for all subjects during the Treatment Extension Period (HH visits are not applicable to subjects in Japan or Korea). For subjects in the active control arm during the Treatment Period, adverse events and concomitant medications information will be collected by telephone call.
17. Serum chemistry panels may include PD parameters (ie, serum phosphorus and ALP), and safety parameters of interest (ie, calcium) to avoid duplication of testing.
18. Both 2-hr and 24-hr urine will be used for measurements of urinary phosphorus, creatinine, and calcium; 2-hr urine will be used for the derivation of TmP/GFR and TRP. For subjects < 5 years of age, spot urine may be collected in place of the 2-hr urine samples for measurements of urinary calcium, phosphorus, and creatinine.
19. Separate dental assessments are not required and will be captured under AEs as dental issues arise. At each clinic visit, an oral examination will be conducted and subjects will be proactively asked if they had any dental events such as dental caries, tooth extraction, root canal, dental abscesses, and gingivitis.
20. Pregnancy testing will be performed on any female subject of childbearing potential who has experienced menarche.

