The study will be conducted in a pediatric population; as such, additional measures including an external, independent DMC have been incorporated into the study design. Where possible, measures to minimize pain and distress to the subject have been considered for this study protocol including the use of home health visits (KRN23 treatment arm only). At every home health visit for subjects in the KRN23 treatment arm, all subjects randomized to the active control arm will receive a phone call to assess adverse events and concomitant medications. Home Health visits are not applicable to subjects in Japan or Korea. Where possible, timing of assessments will be coordinated with standard safety laboratory tests to minimize risk and discomfort and avoid unnecessary duplication of testing. The primary analysis will be at Week 40; analyses at Week 64/EOS I and Week 140/EOS II will assess the durability of treatment effect, additional efficacy outcomes, and long-term safety. The end of the study is defined as the date of the last protocol-specified procedures (including telephone contact) for the last subject in the study.

Figure 7.1.1 provides a schematic of the overall study design.

Figure 7.1.1: UX023-CL301 Study Schema

Pre- and post-prandial serum phosphorus and calcium concentrations will be assessed at a single clinic visit anytime 10 to 14 days after a KRN23 dose; this clinic visit may take the place of a Home Health visit. Approximately 20 subjects, age ≥ 3 years, will fast overnight for a minimum of 8 hours, and fasting serum will be collected prior to a breakfast containing predefined ranges of phosphate, calories, and carbohydrate representative of a typical Western diet for children. Dietary phosphate will be estimated based on the amount of food consumed. Serum samples will be drawn 1 and 2 hours after the completion of the meal.

All radiologic, renal ultrasound, and cardiac (ECG, ECHO) assessments will be administered by personnel trained in the performance of the tests in children, and the results will be interpreted by experts trained in the interpretation of pediatric data. All assessments will be performed and interpreted by staff who are blinded to assigned treatment in the Treatment Period.

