Similarly, historical growth data are of importance and interest. All available recumbent length and standing height data assessed prior to the Screening visit will be collected.

All study visits will be scheduled relative to the Baseline visit, with an allowable variance of ± 3 days for each visit (with the exception of the Screening and Safety Follow-up Visits) to accommodate scheduling. All Screening/Baseline assessments and inclusion/exclusion criteria based on central laboratory results must be satisfied prior to randomization and dosing. KRN23 dosing should occur no sooner than 8 days since the last dose administered.

Subjects may be monitored between site visits through a series of Home Health visits (KRN23 treatment arm only) depending on the preference of the subject and the proximity of the subject to the site. Home Health visits are not applicable to subjects in Japan or Korea. The visit window for Home Health visits is ± 3 days during the Treatment Period. HH visits are not required for subjects randomized to the active control arm because they do not require their medicine to be administered by a healthcare professional. To more closely mimic clinical practice, subjects randomized to the active control arm will only be seen at the site visits. For subjects who discontinue prior to completing the study, every reasonable effort should be made to perform the Early Termination visit procedures within 4 weeks of discontinuation. X-rays will not be performed at the Early Termination visit if post-treatment test(s) have been performed within 6 months of Early Termination. Similarly, the 6MWT will not be performed at the Early Termination visit if post-treatment test(s) have been performed within 3 months of Early Termination or if Early Termination occurs after Week 64.

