7.5.3.12 Dose-limiting Toxicity

A DLT is defined as the occurrence of any of the following:

- Unexpected SAEs occurring during treatment considered to be either definitely, probably, or possibly related to the investigational product or the active control
- A confirmed serum phosphorus level of ≥ 6.5 mg/dL (defined as hyperphosphatemia) at any time after dosing

If a subject experiences a DLT, the planned dosing for that subject will be evaluated by the Investigator and Medical Monitor. The outcome of this investigation will determine the subjects' continuation or withdrawal from the study.

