7.5.3.13 Adverse Events

All AEs will be recorded from the time the informed consent is signed through 12 weeks following the last dose of study drug, unless the subject enrolls in another clinical study of KRN23, is treated with commercially available KRN23, or is treated with KRN23 through another mechanism, at which point the collection of AEs within this study is no longer applicable. However, AEs will continue to be reported either under another KRN23 protocol or per post-approval requirements for safety monitoring, as applicable.

For subjects not continuing KRN23 treatment under commercial use or another mechanism upon completion of study drug treatment or early withdrawal from this study, a Safety Visit will be conducted 12 weeks \pm 1 week after the last dose of KRN23 in this protocol.

The determination, evaluation, reporting, and follow-up of AEs will be performed as outlined in Section 8.5. At each visit, subjects will be asked about any new or ongoing AEs since the previous visit. Assessments of AEs will occur at each visit to the investigational site and at Home Health Visits (KRN23 treatment arm only).

Clinically significant changes from baseline in physical examination findings, vital signs, clinical laboratory parameters, renal ultrasounds, eGFR, and ECGs will be recorded as AEs or SAEs, if deemed appropriate by the investigator.

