7.2.3 Visit Time Windows

Unscheduled visit occurred prior to or on the date of initiation of the first dose will be mapped to the baseline visit if it is the last assessment prior to or on the date of initiation of the first dose; otherwise no mapping will be performed.

Unscheduled visits that occurred after the date of initiation of the first dose will be mapped to the post-baseline scheduled visit with the closest target study day (refer to Section 5.3 for study day definition and Appendix 3 for the schedule of events). If the unscheduled visit is in the middle of two scheduled visits, map to the later scheduled visit. For PD, PK and safety assessments (refer to Section 4.2, 4.3 and 4.4), if the time difference between the unscheduled visit and closest scheduled visit is ≥ 14 days, the unscheduled visit will not be mapped.

For descriptive summary tables, when more than one measurement is mapped to the same scheduled visit, the measurement taken on the scheduled visit will be used if it is not missing, otherwise the one closest to the target day will be used. If two or more visits have equal distances to the target day, then the later one will be used. If more than one measurement is collected on the same day, use the time or the sequence number to select the latest record.

For listings and shift tables in safety analysis, all data points will be included.

Early termination visit will generally follow the same rule as unscheduled visit except for a special case in X-rays. X-rays will not be performed at the early termination visit if the assessment was conducted within 3 months of termination. Hence if a subject has X-rays at both Week 40 and early termination visits, the X-rays on early termination visit will be mapped to Week 64.

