8.5.4.7 PD Analysis

The PD parameters will include serum phosphorus, TmP/GFR, serum 1,25(OH)₂D, TRP, and ALP. All PD analyses will be performed on the PD Analysis Set, unless stated otherwise.

Descriptive statistics of PD parameters and their respective change from baseline and percentage change from baseline will be tabulated by treatment group at each study visit.

The change in serum phosphorus from baseline to mean post-baseline values (average of Week 1, 4, 8, 16, 24, 32 and 40 serum phosphorus for Week 40 analysis and Week 1, 4, 8, 16, 24, 32, 40, 52 and 64 serum phosphorus for Week 64 analysis) will be analyzed using an ANCOVA model. Treatment group, baseline age and RSS total score stratification factors will be included as independent variables, baseline serum phosphorus will be included as a continuous covariate. The estimated difference between KRN23 treatment and active control group will be provided along with 95% CI and p-value. The estimated change from baseline within individual treatment groups will also be provided.

PD endpoints at all scheduled visits will be assessed using the GEE approach as outlined in Section 8.5.1 with change from baseline value as dependent variable, baseline measures and baseline age and RSS total score stratification factors included as independent variables.

The proportion of subjects achieving the normal range (3.2-6.1 mg/dL) will be reported by treatment group at each study visit. Similarly, proportion of subjects achieving TmP/GFR within the normal range (2.6 – 4.4 mg/dL) will be reported by treatment group at each study visit.

A listing containing PD parameters such as serum phosphate level, serum 1,25(OH)₂D, TmP/GFR, TRP, and ALP will be provided for each subject.

Graphs showing the change over time in PD parameters for both observed measure and the respective change from baseline will be provided by treatment group.

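### High phosphorus can be detected at 12 scheduled draws in the KRN23 arm but 9 in control, so the any-time by-arm safety counts need a shared-week line beside them

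*Protocol*

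**What the plan says.** **Contacts.** Schedule of Events footnote 4: "Subjects randomized to the active control arm will visit the clinic at Weeks 1, 4, 8, 16, 24, 32, 40, 52, and 64". Protocol 7.5.1 gives the reason: "To more closely mimic clinical practice, subjects randomized to the active control arm will only be seen at the site visits". Protocol 7.1 pairs the remaining contacts: "At every home health visit for subjects in the KRN23 treatment arm, all subjects randomized to the active control arm will receive a phone call". The call covers adverse events and concomitant medications. Footnote 16 agrees: "For subjects in the active control arm during the Treatment Period, adverse events and concomitant medications information will be collected by telephone call".

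The safety sections read differently. Protocol 7.5.3.13: "Assessments of AEs will occur at each visit to the investigational site and at Home Health Visits (KRN23 treatment arm only". Section 7.5.3.11, on concomitant medications, also names site visits and Home Health visits only. Neither mentions the control calls.

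**Blood draws.** Protocol Tables 2.1 and 2.2 put serum phosphorus and 1,25(OH)₂D at Home Health Weeks 2, 12 and 33. Calcium, creatinine and 25(OH)D are drawn at Home Health Week 2, but not at Weeks 12 or 33.

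**Analyses.** The safety objective (Protocol 6) is a comparison with active control. Protocol 7.6.5 promises, for each laboratory measurement, the number and percentage of subjects with abnormal results. SAP 5.15 makes hyperphosphataemia an event to monitor, and SAP 8.8.1 tabulates its subject incidence by treatment group. For mean phosphorus, by contrast, SAP 8.5.4.7 uses only weeks that both arms attend: "average of Week 1, 4, 8, 16, 24, 32 and 40 serum phosphorus for Week 40 analysis", with Weeks 52 and 64 added for the later analysis. The safety sections have no such rule.

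**The concern.** The percentage of subjects with at least one abnormal value rises with the number of samples taken, even when the underlying risk is the same. The plan matches the weeks for the phosphorus endpoint but not for the safety counts, where unequal sampling bears directly on an any-time incidence. Under Protocol 7.5.3.13 a clinically significant laboratory change can be recorded as an adverse event, so an extra sample can also feed the hyperphosphataemia table. With about 30 children per arm, one more child with a finding moves an arm's percentage by 1/30 = 3.3 points.

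There is also a problem of wording. A site that works from 7.5.3.13 alone would make no adverse event enquiry of a control child between clinic visits, which from Week 40 onward are 12 weeks apart (40, 52, 64).

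**Working it through.** The plan states no figure on this point, so there is nothing to reproduce. The check is a count from Protocol Tables 2.1 and 2.2, with control restricted to the clinic weeks in footnote 4. SAP Tables 10.1 and 10.2 show the same phosphorus and calcium weeks.

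**Scheduled post-baseline draws**

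- Phosphorus: Weeks 1, 2, 4, 8, 12, 16, 24, 32, 33, 40, 52, 64. Removing 2, 12 and 33 leaves the control weeks.
- Calcium and creatinine: Weeks 2, 4, 8, 16, 24, 32, 40, 52, 64. Removing 2 leaves the control weeks.
- 25(OH)D: Weeks 2, 16, 40, 64. Removing 2 leaves the control weeks.

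| Measurement | To Week 40, KRN23 vs control | To Week 64, KRN23 vs control |
|---|---|---|
| Phosphorus | 10 vs 7 | 12 vs 9 |
| Calcium, creatinine | 7 vs 6 | 9 vs 8 |
| 25(OH)D | 3 vs 2 | 4 vs 3 |

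On the shared weeks alone, phosphorus is 7 vs 7 to Week 40 and 9 vs 9 to Week 64.

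**Adverse event contacts**

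- Home Health columns: 11 (Weeks 2 to 30) + 14 (Weeks 33 to 62) = 25. Clinic visits after baseline: 9.
- KRN23: 9 + 25 = 34, all in person. Control: 9 in person + 25 calls = 34.
- To Week 40: KRN23 22 in person; control 7 in person + 15 calls = 22.

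The number of enquiries is the same. The mode differs for 25 of the 34.

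**Which outputs are exposed**

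- SAP 8.8.2 summarises laboratory values at each assessment time point. Shared weeks already sit side by side there, and Weeks 2, 12 and 33 are separate rows. This output is not affected.
- The subject percentages in Protocol 7.6.5 are described per measurement, not per visit. Read as any-time counts, they are affected. SAP 8.8.2 does not say how they will be built.
- The hyperphosphataemia incidence in SAP 8.8.1 is an any-time count and is affected.

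**What the KRN23-only samples measure.** Weeks 2 and 12 are dosing days, and samples are taken before the dose (footnote 11). No dose is scheduled at Weeks 1 or 33. Week 33 is therefore the only scheduled between-dose phosphorus sample after repeated dosing.

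Two limits apply to the count. Home Health visits do not apply in Japan or Korea, and the documents do not say how KRN23 children there are seen in those weeks; the count assumes the same draws. It also omits unscheduled samples.

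**The case against.** The strongest reply is that little can go wrong. Safety summaries are descriptive, with no test to distort. Extra detection counts against the test drug. Home Health visits exist because KRN23 is injected by trained personnel, whereas control medicine needs no professional to give it. The 40-week Phase 2 analysis found no child above the normal phosphorus range (Protocol 5.2.3), and children enter this trial below 3.0 mg/dL. All of this stands and limits the size. It does not make unequal sampling a fair basis for a by-arm percentage.

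A second reply is that restricting the safety comparison to shared weeks would discard Week 33, the sample best placed to show a between-dose rise. This also stands, and it is why the shared-week line should be added and not substituted.

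Several stronger readings are tempting but not supported:

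- **Shift tables.** SAP 7.2.3 says "For listings and shift tables in safety analysis, all data points will be included". A reader might infer that unmatched phosphorus and calcium values enter by-arm shift tables. The only laboratory shift table that SAP 8.8.2 plans is for iPTH, which is drawn at clinic weeks.
- **Dose-limiting toxicity.** The definition includes "A confirmed serum phosphorus level of ≥ 6.5 mg/dL (defined as hyperphosphatemia) at any time after dosing". A reader might infer a by-arm count inflated by extra draws. SAP 5.16 uses the definition to trigger review of that child's dosing, no by-arm table is planned, and the value must be confirmed.
- **Unscheduled draws.** A reader might infer that these add new cases. The protocol-directed ones follow a value already above the upper limit (Protocol 7.4.1), so they cannot supply a child's first high value. Footnote 11 allows unscheduled phosphorus without naming an arm.
- **Fewer adverse event enquiries in control.** The calls match the Home Health visits one for one. Nothing in the documents shows that telephone and in-person enquiry yield different numbers of events here.

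**Conclusion.** The asymmetry is real and confined to any-time subject counts. Phosphorus has three KRN23-only draws (12 against 9 to Week 64), and calcium and creatinine have one (9 against 8). The mean-phosphorus endpoint and the by-visit laboratory summaries are not affected.

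The effect on reported incidence cannot be sized from the documents. A reader might turn 12 against 9 into an excess of about 30% in the KRN23 arm with no true difference. That needs an equal chance of a high value at every draw and independence between draws in the same child. The documents support neither. If high values cluster in the same children, the excess shrinks towards none. Given the Phase 2 experience, which covered ages 5 to 12 only, the effect is probably small, and it would overstate KRN23 harm and not hide it.

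The omission of the control calls from Protocol 7.5.3.11 and 7.5.3.13 is a gap in wording against footnote 16 and Section 7.1, and the passages must be reconciled. If the calls are made as those two places require, the frequency of enquiry is balanced. Overall this is a cheap improvement to a descriptive comparison and does not threaten the trial's conclusions.

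**What to change.** 1. **SAP 8.8.1 and 8.8.2.** Keep the all-data summary. Beside it, add a by-arm subject-incidence line for high phosphorus, calcium and creatinine, restricted to the scheduled weeks both arms share (from Weeks 1, 4, 8, 16, 24, 32, 40, 52 and 64, as drawn). State that the Protocol 7.6.5 percentages are any-time counts, if that is intended.
2. **Flag** abnormal values and adverse events first detected from KRN23-only samples: Weeks 2, 12 and 33, and unscheduled draws.
3. **Keep Week 33** in the safety display.
4. **Protocol 7.5.3.13 and 7.5.3.11.** Name the control-arm telephone calls so that the text agrees with footnote 16 and Section 7.1, and use the same adverse event question at Home Health visits and on the calls.

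The cost is one extra table line, a flag and a short script. There are no added visits or draws, and no data are removed. The change equalises scheduled samples in the added line only. It does not create a control calcium value before Week 4, and it does not remove the difference between in-person and telephone enquiry.
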